Hypothesis 2 (H2): Relative to those treated at UC clinics, eligible 18-75 year-old prediabetes patients with uncontrolled CV risk factors at CDS clinics will have significantly more favorable trajectories in specific CV risk factors, including BP, lipids, smoking, HbA1c, and weight over a median 24-month follow up.

Hypothesis 3 (H3): Relative to those treated at UC clinics, eligible 18 to 75 year-old prediabetes patients at high CV risk treated at CDS clinics will have significantly more favorable patterns of metformin and statinuse over a median 24-month follow up.

Specific Aim 2. Assess the cost of the CDS intervention from the health system (payer) perspective through utilization analyses.

[figure not shown]
Hypothesis 4 (H4): After controlling for demographics and baseline clinical status, eligible patients with prediabetes treated in UC clinics versus CDS clinics will have significantly lower annual healthcare costs from the index date over a median follow up of 24 months.

Specific Aim 3: Describe critical facilitators and barriers for the prediabetes CDS implementation process, outcomes, and future dissemination using a mixed-methods approach.

Note that a previously included cost-effectiveness hypothesis (Hypothesis 5) was not tested due to lack of efficacy of the study intervention. Project results will provide a template for implementation of personalized CDS tools in rural and urban health settings, resulting in more efficient, effective rural healthcare that can be applied across many clinical domains, incorporates patient treatment preferences, and could substantially and sustainably improve the quality of CV care and clinical outcomes of millions of Americans with prediabetes in medically underserved areas.

Overview of Study Implementation Process and Design: The implementation process has four primary components (Figure 1): a) initial organizational engagement; b) adapting and piloting the Prediabetes CDS with Essentia primary care providers and patients; c) a group-randomized controlled study of the adapted CDSin 34 primary care clinics blocked on size and Essentia geographic service area; and d) evaluation of the implementation process and outcomes. It is critical to note that implementation is an iterative process, both in the adaptation

phase and during the randomized controlled trial of implementation and outcomes. Continuous feedback is provided to and

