from organizational leaders, providers, and patients to better understand the facilitators and barriers to implementation and to guide refinements of the CDS.

Group-Randomized Study Eligibility Criteria

Study Sites: The group-randomized controlled study will be implemented in 34 Essentia Health primary care clinics in Minnesota, North Dakota, and Wisconsin. Essentia clinics have used the Epic® EHR since 2004 and have, on average, 14 PCPs (range: 1-56) and 377 prediabetes patients at high CV risk per clinic. Eighty-four percent of the Essentia geographic service area is rural, with 56% of the patient population and 66% of clinics located in this rural area. Average household incomes are less than \$35,000 for 42% of patients, and 45% live in health professional shortage areas.

Study Participants: PCPs and Patients: To participate, PCPs must practice at one of the 34 Essentiaclinics and meet these eligibility criteria: (a) be an adult-care general internist, family physician, non-obstetric nurse practitioner, or physician assistant, and (b) provide ongoing primary care for 15 or more prediabetes adults ages 18-75 with high CV risk. There are currently 441 eligible PCPs which should ensure a more robust understanding of implementation barriers and facilitators in a large PCP community.

To be considered for inclusion in primary or secondary analyses, **patients** must meet all the following eligibility criteria at the time of their indexvisit: (a) be 18-75 years old, (b) have no evidence of diabetes in the previous 12 months (based on lab values, diagnosis codes, use of medications, or on problem list), (c) not be pregnant (d) have the most recent fasting plasma glucose of 100-125 mg/dL or HbA1c 5.7-6.4% within the prior 24 months, (e) have the most recent BMI $\geq 25 \text{ kg/m}^2$, (f) have at least one of the following uncontrolled CV risk factors: current smoking, a diagnosis

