of hypertension with index visit BP ≥140/90 mm Hg or no diagnosis of hypertension but two consecutive BP ≥140/90 mm Hg, or ACC/AHA 10-year CV risk ≥7.5% and LDL either untested or ≥70 mg/dL and not on a statin, (g) no hospice care or chemotherapy for cancer within previous 12 months, and (h) have at least one subsequent primary care visit after the index visit. The patient accrual period (for first index visits) will be 12 months, followed by a 26-month observation period. Thus, patients will have 26 to 38 monthsof follow up, with an expected median of 32 months follow up after the index visit. Pilot data indicate that non- pregnant eligible adults have a median of 6 primary care visits over a 24-month period, ensuring broad inclusion in the analysis. We conservatively estimate an average of 25 eligible patients per consented study PCP with few losses due to death (<1%) in the study period. Few patients switch primary care clinics in Essentia and we accurately match over 98% of patients to a regular PCP. Ultimately, after accounting for all eligibility criteria, we anticipate over 6,600 eligible patients for Aim 1 and Aim 2 analyses. For Aim 1 and Aim 2 analyses we will retrospectively collect CV clinical information and will ask for a waiver of patient consent. The IRB has waived consent in prior and existing evidence-based CDS studies. Patients specifically recruited for focus groups and surveys will be consented and receive

modest compensation for those activities.

Description of Usual Care (UC) and PrediabetesCDS Intervention Conditions.

[figure not shown]
UC Condition. UC clinics and their consented PCPs will have no access to the CDS intervention.

Prediabetes CDS System: The Prediabetes CDS intervention is rooted in a series of antecedent studies that have developed successful forms of CDS for diabetes. The process flow of the intervention is shown in Figure 2.Specific steps in implementation of the Prediabetes CDS intervention are described below.

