Measures of Covariates for Primary and Secondary Analyses: One predictor of CV risk, risk factor, and drug use outcomes is the binary indicator for study condition (CDS or UC). The second key predictor is time elapsed in years between the patient's index visit to each subsequent measurement. Several other measures merit consideration as dependent outcomes, moderators or mediators in primary analyses. These include (a) number of PCP patient encounters, (b) patient characteristics including demographics and pre-intervention clinical values and comorbidities (EHR ICD-10 diagnosis codes and problem lists), and (c) provider characteristics such as age, gender, type of provider, full-time or part-time work status,, specialty board certification status, and proportion of eligible study patients. Patient or provider characteristics may also be used to adjust for covariate imbalance introduced by clinic randomization.

Analysis Plan.

Aim 1 Analytic Approach. Aim 1 pertains to the effectiveness of the Prediabetes CDS intervention, predicting that it will improve the annual rate of change in CV risk (CVR) and individual risk factors relative to UC. Patients age 40-75 at index are included in the Aim 1 analyses because the CDS was programmed to deliver the intervention via treatment recommendations (Figure 2, Step B) to this age group. Rate of change outcomes (e.g., H1, H2) will be tested using random coefficients models in which all available index and post-index outcomes (H1 CV risk, H2 CV risk factors) will be predictedfrom fixed effects for clinic-randomized treatment group, years elapsed since index CVR, the treatment by years elapsed interaction and the index outcome value. Outcomes measured only once per person will follow the same approach, omitting predictors that incorporate years elapsed since index and where warranted including an offset for follow-up time.

Random clinic and patient intercepts will account for clustered observations as appropriate. The link function and error distribution for each model will be determined by the distribution of each outcome. The relationships between years elapsed and CV risk and risk factor outcomes are expected to be linear. The tenability of this assumption will be checked for each outcome and more complex relationships (e.g., non-linear, spline) modeled if warranted.

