Missing data. Because all data elements required for calculating the Aim 1 primary outcome measures(eg, HbA1c, weight, systolic BP, LDL-c, smoking) are drawn from EHR, they will be high quality and available for virtually all tests performed for patients in the analytic dataset. The absence of a measured CV risk factor will result from lack of a factor having been assessed rather than its failure to be documented. As such, missing values will be rare and can be assumed to be missing at random.

Secondary analyses. The primary analytic model is sufficiently flexible to accommodate non-Gaussiandata by specifying alternate error distributions and link functions. As such, secondary efficacy outcomes (eg, treatment mediators and modifiers) and treatment-effect patterns (heterogeneity across demographic and clinical subgroups, persistence of effects) will be analyzed using the Aim 1 approach, with distributional accommodations and model modifications made as needed.

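### The H2 lipid and HbA1c models cannot use patients who lack an index value but have later results, and the claim that missing values are rare is unsupported

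*Combined protocol and SAP*

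**What the plan says.** The Missing data paragraph concludes that "missing values will be rare and can be assumed to be missing at random". Its ground is that the data come from the EHR, and it explains any gap as follows: "The absence of a measured CV risk factor will result from lack of a factor having been assessed rather than its failure to be documented". It gives no expected rate, no handling rule and no sensitivity analysis.

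Other parts of the document bear on this:

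- **Eligibility criterion (f)** counts as an uncontrolled risk factor "ACC/AHA 10-year CV risk ≥7.5% and LDL either untested or ≥70 mg/dL and not on a statin".
- **Eligibility criterion (d)** requires that patients "have the most recent fasting plasma glucose of 100-125 mg/dL or HbA1c 5.7-6.4% within the prior 24 months", so a fasting glucose alone is enough.
- **Hypothesis 2** covers trajectories in specific risk factors, "including BP, lipids, smoking, HbA1c, and weight".
- **Definition and Measurement of Variables, Aim #1** computes the CV risk score with a BMI equation for patients without lipid data. It sets a 48-month look-back for lipids and lists none for HbA1c.
- **Aim 1 Analytic Approach** models "all available index and post-index outcomes" on fixed effects for arm, time, "the treatment by years elapsed interaction and the index outcome value".

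**The concern.** The argument for rarity addresses documentation, while the risk is non-testing. A complete record of tests performed says nothing about patients who were not tested, and the entry rules deliberately let such patients in. The model specification then gives their absence a consequence. A patient with no index LDL or HbA1c has no value for a required covariate, so any later results for that patient cannot be used.

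At stake is whom the H2 lipid and HbA1c results describe. As specified they describe patients already tested at index, while H2 is stated for eligible patients with uncontrolled risk factors. Under criterion (f), untested LDL with sufficient 10-year risk and no statin is one of those factors.

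**Working it through.** **1. Does rarity follow?** The paragraph's premise is that performed tests are recorded and that gaps mean no test was done. Its conclusion is that gaps are few. The premise carries no information on how many patients went untested. Three provisions point the other way: entry on untested LDL, entry on glucose without HbA1c, and a fallback equation for patients without lipids. Restricting Aim 1 to ages 40-75 does not remove the LDL route, because Step C assigns the ACC/AHA 10-year engine to that age group.

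**2. What does the model do with a missing index value?** For patient i in clinic c at time t, the specified model is

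Y(t) = b0 + b1·Arm + b2·t + b3·Arm·t + b4·Y(0) + u_c + v_i + e.

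- If a post-index Y(t) is missing, a likelihood fit uses the remaining rows and is valid under missing at random.
- If Y(0) is missing, the right-hand side is undefined at every t. The model gives Y(0) no distribution as a covariate, so all of that patient's rows are lost, including observed later values.
- For patients with an index value, the t = 0 row has Y(0) on both sides.

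The BMI equation supplies Y(0) for the H1 risk score. Nothing comparable exists for LDL, HDL, total cholesterol or HbA1c as H2 outcomes.

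**3. Size.** The documents give neither an untested share nor an H2 power figure. The nearest calculation is the H1 sample size justification: 15 CDS clinics, 7-11 providers per clinic, 25 patients per provider, 3 scores per patient, patient ICC 0.80, power 0.80, two-sided alpha 0.05.

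- Neff = N / [1 + (n − 1)ρ]
- M = 3·Neff / (1 + 2 × 0.80)
- Minimum detectable slope = (1.96 + 0.84) / √M

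Example with 7 providers and ρ = 0.001: n = 175, N = 2,625, Neff = 2,625/1.174 = 2,236, M = 2,236 × 3/2.6 = 2,580, slope = 2.80/50.8 = 0.055.

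| Clinic ICC | Plan | Recomputed (11 to 7 providers) |
|---|---|---|
| 0.001 | 0.044-0.055 | 0.0458-0.0552 |
| 0.005 | 0.061-0.070 | 0.0625-0.0696 |
| 0.02 | 0.103-0.108 | 0.1034-0.1077 |

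Four of the six values reproduce. All six do with 12 providers at the upper end (0.0443, 0.0614, 0.1027). The gap is minor and has no bearing here.

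As an illustration only, suppose a share q of otherwise usable patients is lost from one H2 model through a missing index value. Power at the full-sample detectable slope is then Φ(2.80 × slope_full / slope_q − 1.96). With 7 providers, ρ = 0.001 and q = 20%, slope_q = 0.0607 and power is about 0.72.

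| Assumed q | ICC 0.001 | ICC 0.005 | ICC 0.02 |
|---|---|---|---|
| 10% | 0.764-0.766 | 0.777-0.782 | 0.791-0.793 |
| 20% | 0.720-0.726 | 0.749-0.760 | 0.779-0.785 |
| 40% | 0.609-0.622 | 0.673-0.697 | 0.744-0.761 |

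This borrows H1 assumptions for H2 and credits each lost patient with three measurements. A patient with no index value may have fewer.

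**4. Testing after index.** The Smartset in Step E groups tests with medications and follow-up, so the intervention could change how often patients are tested. If the 48-month lipid look-back also feeds the H2 values, it exceeds the 26-38 months of follow-up, and one old result could be carried through. A low count of missing values would then not establish adequate measurement. No comparison of testing rates by arm is planned.

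**The case against.** - **The plan never says such patients are excluded.** True: it has no rule for a missing index value, and an analyst might impute. But no imputation is specified, and the model as written cannot be evaluated for these patients.
- **A reader might infer that the rarity claim is false.** The documents do not show that. Untested LDL is one branch of one of three risk-factor routes, it also requires 10-year risk of at least 7.5%, and the lipid look-back is long. The claim is unsupported, not disproved.
- **A reader might infer that missing at random fails.** Not shown. Testing that depends on arm, earlier values or visits is compatible with it, provided those are observed and in the model.
- **A reader might infer a biased comparison.** Absence of a test before index should be roughly balanced by randomisation. Post-index testing could differ by arm, but the documents do not show that it does.
- **A reader might apply an assumed untested share to the 6,600 anticipated patients.** That count is given for Aims 1 and 2 under entry criteria spanning ages 18-75, while Aim 1 is limited to 40-75. It would also include patients never tested later, whom no model recovers.
- **The paragraph may concern only the primary outcome, and HbA1c is loosely placed.** Its examples include HbA1c, which is an H2 outcome. The Aim #1 measurement list for H2 does omit HbA1c although Hypothesis 2 names it, so the text should be aligned. The HbA1c part of this point rests on the fasting-glucose route, not on untested LDL.

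**Conclusion.** The point holds for H2 lipids and HbA1c. The statement that missing values will be rare does not follow from the reasoning given and is in tension with the entry criteria and the fallback equation. Conditioning on the index value discards usable later results from patients the criteria deliberately include.

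The cost is mainly precision and generalisability. Under the illustrative assumptions it is modest at 10% loss (power about 76-79% instead of 80%) and larger at 40% (about 61-76%). The real share cannot be computed from the documents. H1 is largely protected by the BMI equation. The conclusion assumes that the model is fitted as written, with no imputation of the index value.

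**What to change.** For H2 lipids and HbA1c:

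1. Remove the index value as a covariate and keep it only in the outcome vector of the random coefficients model. Patients with only post-index results then contribute, and the index value no longer appears on both sides.
2. Either retain the treatment main effect, which needs no baseline assumption, or constrain index means to be equal across arms. The constraint is an assumption to check: 34 clinics were randomised, patients accrued afterwards, and the plan itself anticipates covariate imbalance.
3. Report, by arm, the proportion with an index value and the post-index testing rate for each outcome.
4. Add a delta-adjusted sensitivity analysis in which unmeasured values are shifted over a stated range, including different shifts by arm.
5. Delete the word rare from the Missing data paragraph and state the rule for a missing index value.

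The cost is revised text and standard mixed-model code on EHR data already held. Because this version already reports lack of efficacy (the note on the dropped cost-effectiveness hypothesis), the re-analysis should be labelled supplementary and not replace the specified H2 model.
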